Methodology:	The testing methods are based on the standardized test method ASTM E1173-15, Evaluation of Preoperative, Precatheterization, or Preinjection Skin Preparations . Following a 14-day restriction period, subjects will be sampled for baseline, 30-seconds, 10-minutes, and 6-hours microbial reduction evaluations post-product application. Subjects will be sequestered for the 6-hour evaluation. Test day baseline criteria will be set at: abdomen: $3.0 - 5.5 \log_{10} \text{CFU/cm}^2$, and inguen: $5.0 - 7.5 \log_{10} \text{CFU/cm}^2$.
Number of Subjects:	A sufficient number of subjects will be entered into testing to complete 50 subjects per each of the 2 test and 1 control materials. A minimum of 75 subjects meeting the test day baseline criteria will test bi-laterally (150 abdomen and inguinal sites; 50 abdomen and inguinal sites per test and control materials).
Main Criteria for Inclusion:	A sufficient number of overtly healthy subjects at least 18 years of age will be admitted into the study so that a minimum of 75 subjects complete the study. Insofar as possible, the groups of subjects selected will be of mixed sex, age, and race. The subject recruiters will verbally and/or visually verify with subjects that the skin of the abdomen and inguen are free from clinically evident dermatoses, injuries, or any other disorders that may compromise the subject or the study.
Duration of treatment:	For each subject, two of the three test materials will be applied bi-laterally to abdomen and inguinal sites, a single time.

Name of Sponsor: Professional Disposables International, Inc. (PDI)	
Name and Concentration of Test Product Active Ingredients: 26 mL Chlorhexidine Gluconate 3.15% (w/v) and Isopropyl Alcohol 70% (v/v) solution 5.1 mL Chlorhexidine Gluconate 3.15% (w/v) and Isopropyl Alcohol 70% (v/v) solution	Protocol Number 1810480-103.01

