9.2 Discussion of Study Design, Including Choice of Sample Size

The sample size of a minimum of 100 subjects treated per test material is required for performing this type of evaluation based on the 2017 FDA 21 CFR Part 310, *Safety and Effectiveness of Health Care Antiseptics; Topical Antimicrobial Drug Products for Over-the-Counter Human Use*, Final Rule (December 20, 2017). For this pilot study, only a minimum of 50 subjects treated per test material will be evaluated to determine if a study utilizing 100 subjects will meet the requirements in a pivotal study.

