9.4.3 Method of Assigning Subjects to Treatment Groups

The three test materials will be assigned randomly to the test sites per a computer-generated randomization schedule, such that two of the three test materials are used on each subject at the abdomen and/or inguinal sites, one test material on one side, and another test material on the opposite side of the subject. The randomization schedule will be continued until it is determined that the required sample sizes are fulfilled.

The specific sites for post-application sampling (i.e., 30 seconds, 10 minutes, and 6 hours after skin preparation on the abdominal and inguinal test sites) will be assigned according to a computer-generated randomization scheme.

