9.7.1 Statistical Methods

The Minitab® Version 18 statistical computer package will be used for all statistical calculations.

Non-Inferiority Analysis

An analysis of the data will be performed to determine the non-inferiority of the two test products to the Positive Control. Separate analyses will be performed for data sets for both the abdomen and the inguinal test sites and for the 30-seconds and 10-minutes post-application sample time. Only those data from sites meeting the baseline criteria (3.0 - 5.5 \log_{10} CFU/cm² from the skin of the abdomen and 5.0 - 7.5 \log_{10} CFU/cm² from the skin of the inguen) will be used in the analysis.

The statistic to be used is a multiple linear regression with one quantitative and one qualitative predictor. It has the form:

$$\hat{y} = B_0 + B_1 x_1 + B_2 x_2 + e$$

where:

\hat{y} = \log_{10} Recoveries

B_0 = y intercept

B_1 = Regression slope

B_2 = Difference between the two products

x_1 = \log_{10} Baseline

x_2 = Products

1, if Test Product

2, if Positive Control

e = Error term

The average treatment effect (ATE) is the mean of the 95% confidence interval. For the non-inferiority test, the upper bound of the 95% confidence interval must be equal to or less than 0.5 \log_{10} .

For the non-inferiority test:

$$\bar{x}_C - \bar{x}_T \leq 0.5$$

where:

\bar{x}_T = mean of the test product

\bar{x}_C = mean of the positive control product

0.5 = non-inferiority margin

Descriptive statistics will be generated, including sample sizes, means, standard deviations, and ranges of the recovery data.

Sample Size Determination Analysis

When the study is complete, the PASS 16 statistical package will determine the number of subjects used in a pivotal study for the abdominal and inguinal regions.

The formula that will be used is:

$$n \geq \frac{2 s^2 (z_{\alpha/2} + z_{\beta})^2}{0.5^2}$$

where:

n = minimum number of subjects employed in the study

2 = number of products tested; 3 test materials (Test Product #1, Test Product #2 and Positive Control)

s^2 = the largest variance of the two products tested at the abdominal or inguinal sites

$z_{\alpha/2} = 1.96$ (z-scale) for $1 - 0.05 = 95\%$ confidence of Type I error

$z_{\beta} = 0.842$ (z-scale) for $1 - 0.20 = 0.80\%$ confidence of Type II error

0.5 = Detection level requirement

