9.7.2 Determination of Sample Size

The sample size of a minimum of 100 subjects treated per test material is required for performing this type of evaluation based on the 2017 FDA 21 CFR Part 310, *Safety and Effectiveness of Health Care Antiseptics; Topical Antimicrobial Drug Products for Over-the-Counter Human Use*, Final Rule (December 20, 2017). For this pilot study, only a minimum of 50 subjects treated per test material will be evaluated to determine if a study utilizing 100 subjects will be likely to meet the requirements in a pivotal study.

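### The pivotal sample-size formula in Section 9.7.1 yields a count per test material per region, but n is defined as a study total and no conversion is given

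*Combined protocol and SAP*

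**What the plan says.** Under the sample-size heading of Section 9.7.1, the protocol states that once the pilot is complete "the PASS 16 statistical package will determine the number of subjects used in a pivotal study for the abdominal and inguinal regions". It then prints the formula n ≥ 2s²(z_α/2 + z_β)²/0.5², with z values of 1.96 and 0.842, and defines its terms:

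- n: "n = minimum number of subjects employed in the study"
- the multiplier: "2 = number of products tested; 3 test materials (Test Product #1, Test Product #2 and Positive Control"
- the variance term, to be taken from the pilot data: "the largest variance of the two products tested at the abdominal or inguinal sites"

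The analysis that this n must support is also in Section 9.7.1. It is a separate regression for each region and each of the two early sampling times, adjusted for baseline, using only sites that pass the baseline limits.

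Elsewhere the plan counts per material. Section 9.4.3 says that "two of the three test materials are used on each subject at the abdomen and/or inguinal sites", one per side. The synopsis translates 75 bilateral subjects into "150 abdomen and inguinal sites; 50 abdomen and inguinal sites per test and control materials". Section 9.2 states, with reference to the 2017 rule: "The sample size of a minimum of 100 subjects treated per test material is required".

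**The concern.** The formula has the form of a per-group sample size, yet its result is labelled as the size of the whole study. The reason given for the 2, a number of products, hides this, because it suggests that the products have already been counted. A reader who follows the definitions would report n as the pivotal total.

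Finding the pivotal sample size is a stated objective of the pilot (synopsis and Section 8.0), and this is the formula the plan says will be used. If the pivotal study kept two of three materials per subject, a total of n subjects would give each material only 2n/3 sites per region, and the 0.80 power stated in Section 9.7 would be missed.

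**Working it through.** **Inputs from the documents.** Power 0.80, alpha 0.05 and difference 0.5 log10 (Section 9.7); z values 1.96 and 0.842 (Section 9.7.1); two of three materials per subject (Section 9.4.3); 75 subjects and 50 sites per material (synopsis); minimum of 100 per material (Sections 9.2 and 9.7.2).

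**Inputs not in the documents.** The SD, the baseline-to-post correlation r and the pivotal layout. Values below are assumptions. Sites are treated as independent, the true difference is 0, and both products have variance s².

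**1. The plan's own figure.** 75 × 2/3 = 50 sites per material per region. This reproduces; subjects to sites per material is 75/50 = 1.5.

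**2. What the formula returns.** (1.96 + 0.842)² = 7.851, so n = 2 × 7.851 × s²/0.25 = 62.81 s². The variance of a difference between two independent means with n each is s²/n + s²/n = 2s²/n. Setting 0.5 = (1.96 + 0.842) × √(2s²/n) and solving for n gives the printed formula, so the 2 is that variance factor. At SD 1.0, n = 63. With 63 per product, power = Φ(0.5/√(2/63) − 1.96) = 0.801 (simulation 0.802). The stated power is reached when n is the count per product.

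**3. Sites versus subjects.** Within a region a material is used on at most one side of a subject, so sites per material equal subjects treated per material. The discrepancy is between a per-material count and a study total.

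**4. n taken as the total, two of three per subject, no minimum.** Each material gets 2n/3 sites. With error variance s²(1 − r²), power = Φ(√((2/3)/(1 − r²)) × 2.802 − 1.96).

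| Meaning of s² | Power |
|---|---|
| Error variance (r = 0 in the formula) | Φ(2.288 − 1.96) = 0.628 |
| Raw variance, r = 0.3 | Φ(2.398 − 1.96) = 0.669 |
| Raw variance, r = 0.5 | Φ(2.642 − 1.96) = 0.752 |
| Raw variance, r = 0.577 | 0.800 |

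At SD 1.0 this means 63 subjects and 42 sites per product: power 0.630 (simulation 0.630).

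**5. With the 100-per-material minimum honoured.** Under this layout that means at least 150 subjects. 100 per material gives 0.80 power up to SD = √(100/(62.81(1 − r²))): 1.26 (error variance), 1.32 (raw, r = 0.3) or 1.46 (raw, r = 0.5). Above that, with m = max(100, 2n/3) sites per material:

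| SD | n | Subjects if n is the total, max(150, n) | Subjects at 1.5n | Power if n is the total: error / raw r = 0.3 / raw r = 0.5 |
|---|---|---|---|---|
| 1.4 | 124 | 150 | 186 | 0.714 / 0.754 / 0.830 |
| 1.5 | 142 | 150 | 213 | 0.654 / 0.695 / 0.777 |
| 1.75 | 193 | 193 | 290 | 0.630 / 0.671 / 0.754 |

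**6. Meaning of s².** If s² is the raw variance, the formula overstates the n that the baseline-adjusted model needs by 1/(1 − r²): 1.10 at r = 0.3 and 1.33 at r = 0.5. Applied per material, n then gives Φ(√(1/0.75) × 2.802 − 1.96) = 0.90 power at r = 0.5.

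**The case against.** No number in the plan is wrong. The constants are used correctly, the pilot arithmetic reproduces, and correcting the account of the 2 changes no result. The synopsis and Sections 9.2, 9.3 and 9.7.2 all count per material, so the statistician running PASS is likely to apply n that way. The harm needs three things together: a literal reading of n, a pivotal study that repeats two-of-three allocation, and a fairly large SD. The documents give neither the SD nor the layout. The layout may well change, since Section 7.0 also requires superiority to a negative control, which Section 9.1 leaves out of this pilot. Taking the larger variance is itself conservative: if the other product's SD were 20% lower (an assumption), the mean variance would be 0.82s², and the 63% would become Φ(√((2/3)/0.82) × 2.802 − 1.96) = 71%.

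All of this stands and limits the practical consequence. It does not correct the definition in Section 9.7.1 or supply the missing conversion.

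Two stronger readings are tempting but unsupported:

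- A reader might take the line that pairs 2 products with 3 test materials as a self-contradiction. Section 4.0 defines a test material as a test product or the positive control, and Section 9.1 speaks of two test products among three test materials, so the line can be read consistently. The fault is the reason it gives for the 2.
- A reader might take the sentence in Section 9.7.2 that 50 per material are "evaluated to determine if a study utilizing 100 subjects will be likely to meet the requirements in a pivotal study", and its near twin in Section 9.2, as a second confusion of units. Both follow a statement of 100 per test material and set that figure against 50 per test material, so in context the 100 is per material.

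**Conclusion.** The definitions of n and of the 2 in Section 9.7.1 are wrong as written, and the step from n to a subject total is missing. That conclusion needs no assumption about SD or layout.

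The size of the consequence is conditional. Used literally as a total under two-of-three allocation, n would under-size each material by one third, and power would be about 63% (error variance) or 67% to 75% (raw variance, r = 0.3 to 0.5) before any minimum. It disappears if n is applied per material, if each subject receives both compared products, if s² is the raw variance and r is about 0.58 or more, or while the 100-per-material minimum governs. A reader might infer that the pivotal study will be underpowered; the documents do not support that, because they fix neither the SD, nor the correlation, nor the pivotal allocation. The pilot's own enrolment and non-inferiority analysis do not depend on this formula. The point is worth fixing because it concerns a stated deliverable and the correction is nearly free.

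**What to change.** In Section 9.7.1:

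1. Define n as the minimum number of evaluable sites per test material, per anatomical region.
2. Explain the 2 as arising from the variance of a difference between two independent means.
3. Add that the subject total follows from the pivotal allocation. Under equal allocation, evaluable subjects = n (not below 100 per material) × number of materials / materials per subject, which is 1.5n if two of three is retained. Allowance for baseline failures comes on top.
4. State whether s² is the raw variance of the recoveries or the residual mean square of the baseline-adjusted regression.

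The conversion covers the non-inferiority comparison only; the pivotal protocol must also size the superiority comparison.

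The cost is a few lines of text, with no new data and no change to the pilot's conduct. Under two-of-three allocation with the minimum honoured, the reported total stays at 150 while n is 100 or less (SD up to about 1.26) and rises above that, for example to 213 instead of 150 at SD 1.5. If s² remains the raw variance, 1.5n is conservative by a factor of 1/(1 − r²).

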9.7.2 Determination of Sample Size

The sample size of a minimum of 100 subjects treated per test material is required for performing this type of evaluation based on the 2017 FDA 21 CFR Part 310, *Safety and Effectiveness of Health Care Antiseptics; Topical Antimicrobial Drug Products for Over-the-Counter Human Use*, Final Rule (December 20, 2017). For this pilot study, only a minimum of 50 subjects treated per test material will be evaluated to determine if a study utilizing 100 subjects will be likely to meet the requirements in a pivotal study.

9.8 Changes in the Conduct of the Study or Planned Analyses

Neither the Investigators nor the Sponsor will modify or alter this protocol without first obtaining agreement from the other parties with one exception: when necessary to eliminate an apparent immediate hazard to the subject. All protocol modifications including, but not limited to, changes in the Principal Investigator, inclusion/exclusion criteria, number of subjects to be enrolled, study sites, or procedures must be submitted to the GIRB as a written amendment for review and approval prior to implementation.

10.0 STUDY SUBJECTS

10.1 Disposition of Subjects

A written consent form will be obtained from each subject and filed by the Investigator with the subject's records, in accordance with 21 CFR Parts 50 and 56.

The Investigator may discontinue individual subjects from the study at any time. Subjects may voluntarily withdraw from the study at any time. The Investigator or designee will provide a written report on the appropriate study document describing the reason for discontinuance and the date of discontinuance. The discontinued or withdrawn subject who participated in treatment may not re-enter the study. The Investigator will provide a disposition table that specifies the number of subject's enrolled, randomized, treated, and discontinued as well as reasons for discontinuations.

In order to implement a valid revocation of authorization to use and disclose private health information, the subject or their representative **must** make the request in writing to BioScience Laboratories, Inc., [name]. The revocation cannot stop the use or disclosure of information that has been collected prior to the revocation, is needed to ensure complete and accurate study results, or is required by law or government regulation (e.g. reporting adverse events, etc.). Revocation of an authorization may not be used to withhold normal medical care from the subject, but will make the subject ineligible to receive the study treatment or care.

10.2 Protocol Deviations

This study will be conducted as described in this Protocol, except for an emergency situation in which the protection, safety, and well-being of the subject requires immediate interventions, based on the judgment of the Principal Investigator. In the event of a significant deviation from the Protocol due to an emergency, accident, or mistake, the Investigator or designee will document the details of the situation and any subsequent decisions. All deviations from the Protocol or approved amendments shall be documented by BSLI. Any deviation to the protocol that may have an effect on the safety or rights of the subjects must be reported immediately (within 24 hours) to the local GIRB and sponsor representative. Any deviation that may compromise the statistical analysis of the study must be reported immediately (within 24 hours) to the sponsor representative.

The Sponsor or the Investigator has the right to discontinue the study at any time for medical and/or administrative reasons. This should occur after mutual consultation, where possible.

11.0 SAFETY EVALUATION

11.1 Safety Assessments

The subject's safety will be monitored by evaluations of reactions observed on the skin of the test sites and any adverse reactions. Adverse reactions will be fully documented, reported as an Adverse Event, and followed to resolution.

11.2 Evaluation of Test Sites on Completion

Skin reactions will be evaluated prior to and post-product application (baseline, 30-seconds, 10-minutes, and 6-hours) using the following Skin Irritation Scoring System (Draize).

SKIN IRRITATION SCORING SYSTEM (Draize)

Erythema	0	No reaction
	1	Mild and/or transient redness limited to sensitive area
	2	Moderate redness persisting over much of the test material-exposed area
	3 *	Severe redness extending over most or all of the test material-exposed area
Edema	0	No reaction
	1	Mild and/or transient swelling limited to sensitive area
	2	Moderate swelling persisting over much of the test material-exposed area
	3 *	Severe swelling extending over most or all of the test material-exposed area
Rash	0	No reaction
	1	Mild and/or transient rash limited to sensitive area
	2	Moderate rash persisting over much of the test material-exposed area
	3 *	Severe rash extending over most or all of the test material-exposed area
Dryness	0	No reaction
	1	Mild and/or transient dryness limited to sensitive area
	2	Moderate dryness persisting over much of the test material-exposed area
	3 *	Severe dryness extending over most or all of the test material-exposed area

* = A score of 3 in one or more of the conditions evaluated represents significant irritation and qualifies as an Adverse Event.

11.3 Adverse Events

Adverse events will be captured for all subjects from the time of informed consent to the time of subject discharge from the study. Adverse events will be categorized in relationship to the test materials that were applied. Medical facilities/personnel are in close proximity.

In the event that either the Principal Investigator or the Sponsor determines that continuation of the study poses a hazardous risk of serious injury or death to the subjects, the study will be stopped.

11.3.1 Adverse Event/Experience

An Adverse Event/Experience is any unexpected or undesirable experience occurring to a subject during a study, which may or may not be related to the test materials. All adverse event/experiences will be recorded and reported using appropriate Adverse Event documentation according to the Standard Operating Procedures of the laboratory.

All adverse events, regardless of severity or the cause/effect relationship, are to be recorded. The severity of the effect will be noted as "Mild," "Moderate," or "Severe" according to the following definitions:

Mild	Awareness of signs or symptom, but easily tolerated.
Moderate	Discomfort to a degree as to cause interference with normal daily life activities and /or requiring medication.
Severe	Incapacity with inability to work or do usual daily life activities and requiring medical attention/intervention.

11.3.2 Causal Relations of Adverse Event/Experience

When determining the causal/effect relationship to a test material, the relationship will be described as "*None*," "*Possible*," "*Probable*," or "*Definite*." The following definitions will be utilized:

None	No association to the test materials. Related to other etiologies such as concomitant medications or conditions or subject's known clinical state.
Possible	Uncertain association. Other etiologies are also possible.
Probable	Clear-cut association with improvement upon withdrawal of the test materials. Not reasonably explained by the subject's known clinical state but not an anticipated event.
Definite	An adverse event with a clear-cut temporal association and laboratory confirmation if possible.

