Each subject who volunteers to participate in this study will be required to remain/be sequestered at the test facility through the 6-hours post-treatment sampling. Following collection of the last 6-hour \pm 30 minutes post-product application sample of a test site, the remaining test material will be wiped/cleansed from the test site with a mild soap and/or tap water; test sites will be dried with paper towels.

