11.3.7 Anticipated Reactions

Minimal risks to the study subjects are anticipated during the study. The risks associated with this study are primarily related to application of the test materials. Reactions to adhesives are also possible. Mild skin irritation or mild local irritant reactions such as burning and itchiness are anticipated. Although not anticipated, more severe reactions might occur, including moderate to severe erythema, swelling, cracking, peeling, or, in rare cases, blistering and/or an allergic reaction. Other anticipated reactions that may occur may result from testing procedures. Irritation and/or folliculitis may occur after clipping. A mild or moderate abrasion may occur from the Cylinder Sampling Technique.

A Chlorhexidine gluconate (CHG) solution will be utilized during testing. CHG can cause a rare, but serious allergic reaction that may be life-threatening. Subjects will be instructed to seek immediate emergency medical help if they experience any of the

following symptoms: hives, severe skin rash, wheezing, difficulty breathing, cold sweats, feeling light-headed, or swelling of the face/lips/tongue/throat.

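### The Probable causality grade excludes anticipated events and Definite has fewer binding conditions, so an anticipated reaction with a likely but uncertain link has no fitting grade

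*Combined protocol and SAP*

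**What the plan says.** Section 11.3 requires adverse events to be categorized by their relationship to the test materials, and section 11.3.2 supplies four grades. Apart from None, they are:

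- Possible, the lowest of the three, is for an association that is uncertain and may have other causes.
- Probable, the middle grade, asks for a clear association that improves when the material is withdrawn. Its second sentence adds: "Not reasonably explained by the subject's known clinical state but not an anticipated event".
- Definite, the top grade, is worded as follows: "An adverse event with a clear-cut temporal association and laboratory confirmation if possible".

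Section 11.3.7 states: "Mild skin irritation or mild local irritant reactions such as burning and itchiness are anticipated". It also names adhesives, clipping and cylinder sampling as possible sources of local reactions, and describes more severe skin reactions as possible but not anticipated. Section 11.3.4 defines an unexpected event separately, by reference to the labeling, the investigator's brochure and section 11.3.7.

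On timing, the synopsis provides for a single application. Section 11.2 schedules skin scores at baseline, 30 seconds, 10 minutes and 6 hours. Section 9.4.5 provides that, after the last 6-hour sample of a site, "the remaining test material will be wiped/cleansed from the test site with a mild soap and/or tap water". Section 11.1 says that adverse reactions are followed until they resolve; section 11.3.5 gives that undertaking only for serious or unexpected events.

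**The concern.** A causality grade should express how strong the evidence is that the product caused the event. Whether the event was foreseen is a different question, and section 11.3.4 already asks it. Putting expectedness into one middle grade breaks the scale for the very reactions that the protocol foresees from the products.

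A second weakness is that the top grade is not built on the grade below it. Definite can be reached on timing alone. In this trial several other causes act on the same skin around the same time: the sampling cylinder may abrade it, adhesives may provoke a reaction, and clipping may irritate it.

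At stake is the consistency of the causality categories. The synopsis rests safety on adverse event reporting and skin assessment, so two assessors with the same evidence should reach the same grade.

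**Working it through.** There is no figure to reproduce and no arithmetic beyond counting conditions. The check sets the definitions beside the rest of section 11 and section 9.4.5.

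**Step 1. Conditions in each grade (section 11.3.2).**

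| Condition | Possible | Probable | Definite |
|---|---|---|---|
| Strength of association | Uncertain | Clear-cut | Clear-cut in time |
| Improvement on withdrawal | No | Required | No |
| Not explained by clinical state | No | Required | No |
| Not an anticipated event | No | Required | No |
| Laboratory confirmation | No | No | Only if possible |

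Probable has four binding conditions. Definite has one, plus confirmation where it can be obtained. The scale therefore does not rise from Probable to Definite.

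**Step 2. Grades open to an anticipated reaction.** Take itchiness at a treated site, which section 11.3.7 lists as anticipated. Suppose the evidence favors the product but is not conclusive. Probable is closed by its last clause. Possible understates the evidence, because it is for an uncertain association. Definite overstates it. Two of the three related grades remain, and neither fits.

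**Step 3. Competing causes.** Section 11.3.7 lists reactions from adhesives, clipping and cylinder sampling. Under section 9.4.5 a dressing covers the 6-hour site after the 10-minute sample. A site reaction soon after application may thus have a product cause or a procedural one. Definite does not ask the assessor to exclude the procedural cause. Probable asks only about the subject's clinical state, so it does not name study procedures either.

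**Step 4. The withdrawal condition.** Three skin scores are scheduled after application (30 seconds, 10 minutes, 6 hours). The only planned removal follows the last 6-hour sample, and no score is scheduled after it. That the 6-hour score precedes cleansing is inferred from their shared time point; the text does not state the order. Improvement after removal can still be recorded during the follow-up in section 11.1. What is unclear is whether a non-serious, anticipated reaction gets that follow-up, because section 11.3.5 is narrower.

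**Step 5. Where the grade is used.** Section 11.3 requires the categorization. The 2-business-day rule in section 11.3.6 turns on whether an event is related to product usage or needs medical treatment. It does not say which grades count as related. Serious or unexpected events are reported immediately whatever their grade.

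**The case against.** The strongest reply is that this is a drafting slip with little practical effect, and several parts of that reply stand.

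- A reader might infer that the commonest expected reactions are misclassified. The documents do not support this. They give no reaction frequencies, and exclusion from one grade is not misclassification. Burning on one side from the moment of application, for example, meets Definite as written.
- Section 11.3.7 says that the more severe reactions, such as moderate to severe erythema and swelling, are not anticipated, so the clause does not bar them from Probable. Some doubt remains, because they are listed in the very section that section 11.3.4 uses to define what is unexpected.
- In section 11.2 it is a skin score of 3 that qualifies as an adverse event, so milder scores may never be graded for causality. This does not dispose of the point: section 11.3.1 counts any undesirable experience and records events of every severity.
- A reader might infer that the withdrawal condition can never be observed. Section 11.1 answers that: improvement can be documented outside the scheduled scores.
- A reader might infer that a relatedness table becomes uninterpretable or that reporting changes. No such table is specified, and no reporting rule cites the Possible, Probable or Definite grades.

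None of this removes the literal exclusion in Probable or the lower threshold for Definite.

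**Conclusion.** The point holds in a limited form. As written, an anticipated reaction with a likely but not certain link to a test material has no fitting grade and must be moved down or up. Definite is reached on one binding condition against four for Probable, and it does not require other causes to be excluded. The causality categorization may therefore be inconsistent between assessors.

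The size in events cannot be given, since no reaction rates are stated. No efficacy result or sample size depends on it. The conclusion assumes that the definitions are applied literally and that at least some mild anticipated reactions are recorded as adverse events, which section 11.3.1 allows. It is worth correcting because the change is specific and nearly free.

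**What to change.** In section 11.3.2:

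1. Remove the expectedness clause that closes the definition of Probable, and leave expectedness to section 11.3.4.
2. Make Definite include the requirement that the event is not reasonably explained by another cause, worded to cover study procedures as well as the subject's clinical state. Keep laboratory confirmation conditional on its being possible. Burning or itching may have no laboratory test, so compulsory confirmation could shut these reactions out of the top grade.
3. Treat improvement after removal as supporting evidence when it is observed during follow-up, since no skin score is scheduled after removal.

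Sections 11.1 and 11.3.5 should also be reconciled on which events are followed to resolution.

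The cost is a few lines of protocol text, a matching change to the adverse event form, and a written amendment approved by the IRB before use, as section 9.8 requires. No visits or measurements are added.
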